10.3.1 Definition of AE

AE definition

- An AE is any untoward medical occurrence in a clinical study participant, temporally associated with the use of study intervention, whether or not considered related to the study intervention.
- NOTE: An AE can therefore be any unfavorable and unintended sign (including an abnormal laboratory finding), symptom, or disease (new or exacerbated) temporally associated with the use of a study intervention.
- NOTE: For purposes of AE definition, study intervention (also referred to as Sponsor's product) includes any pharmaceutical product, biological product, vaccine, diagnostic agent, or protocol specified procedure whether investigational or marketed (including placebo, active comparator product, or run-in intervention), manufactured by, licensed by, provided by, or distributed by the Sponsor for human use in this study.

Events meeting the AE definition

- Any abnormal laboratory test results (hematology, clinical chemistry, or urinalysis) or other safety assessments (eg, ECG, radiological scans, vital signs measurements), including those that worsen from baseline, considered clinically significant in the medical and scientific judgment of the investigator.
- Exacerbation of a chronic or intermittent pre-existing condition including either an increase in frequency and/or intensity of the condition.
- New conditions detected or diagnosed after study intervention administration even though it may have been present before the start of the study.
- Signs, symptoms, or the clinical sequelae of a suspected drug-drug interaction.
- Signs, symptoms, or the clinical sequelae of a suspected overdose of either study intervention or a concomitant medication.
- For all reports of overdose (whether accidental or intentional) with an associated AE, the AE term should reflect the clinical symptoms or abnormal test result. An overdose without any associated clinical symptoms or abnormal laboratory results is reported using the terminology "accidental or intentional overdose without adverse effect."
- Any new cancer or progression of existing cancer.

Events NOT meeting the AE definition

- Medical or surgical procedure (eg, endoscopy, appendectomy): the condition that leads to the procedure is the AE.
- Situations in which an untoward medical occurrence did not occur (social and/or convenience admission to a hospital).
- Anticipated day-to-day fluctuations of pre-existing disease(s) or condition(s) present or detected at the start of the study that do not worsen.
- Surgery planned prior to informed consent to treat a pre-existing condition that has not worsened.
- Refer to Section 8.4.6 for protocol-specific exceptions.

10.3.2 Definition of SAE

If an event is not an AE per definition above, then it cannot be an SAE even if serious conditions are met.

An SAE is defined as any untoward medical occurrence that, at any dose:

- **Results in death**
- **Is life-threatening**
- The term “life-threatening” in the definition of “serious” refers to an event in which the participant was at risk of death at the time of the event. It does not refer to an event, which hypothetically might have caused death, if it were more severe.

1. Requires inpatient hospitalization or prolongation of existing hospitalization

- Hospitalization is defined as an inpatient admission, regardless of length of stay, even if the hospitalization is a precautionary measure for continued observation. (Note: Hospitalization for an elective procedure to treat a pre-existing condition that has not worsened is not an SAE. A pre-existing condition is a clinical condition that is diagnosed prior to the use of an MSD product and is documented in the participant’s medical history.)

2. Results in persistent or significant disability/incapacity

- The term disability means a substantial disruption of a person’s ability to conduct normal life functions.

- This definition is not intended to include experiences of relatively minor medical significance such as uncomplicated headache, nausea, vomiting, diarrhea, influenza, and accidental trauma (eg, sprained ankle) that may interfere with or prevent everyday life functions but do not constitute a substantial disruption.

3. Is a congenital anomaly/birth defect

- In offspring of participant taking the product regardless of time to diagnosis.

4. Other important medical events

- Medical or scientific judgment should be exercised in deciding whether SAE reporting is appropriate in other situations such as important medical events that may not be immediately life-threatening or result in death or hospitalization but may jeopardize the participant or may require medical or surgical intervention to prevent 1 of the other outcomes listed in the above definition. These events should usually be considered serious.

Examples of such events include invasive or malignant cancers, intensive treatment in an emergency room or at home for allergic bronchospasm, blood dyscrasias or convulsions that do not result in hospitalization, or development of drug dependency or drug abuse.

10.3.3 Additional Events Reported

Additional events that require reporting

In addition to the above criteria, AEs meeting either of the below criteria, although not serious per ICH definition, are reportable to the Sponsor.

- Is a cancer
- Is associated with an overdose

10.3.4 Recording AE and SAE

AE and SAE recording

- When an AE/SAE occurs, it is the responsibility of the investigator to review all documentation (eg, hospital progress notes, laboratory, and diagnostics reports) related to the event.
- The investigator will record all relevant AE/SAE information on the AE CRFs/worksheets at each examination.
- It is not acceptable for the investigator to send photocopies of the participant's medical records to the Sponsor in lieu of completion of the AE CRF page.

- There may be instances when copies of medical records for certain cases are requested by the Sponsor. In this case, all participant identifiers, with the exception of the participant number, will be blinded on the copies of the medical records before submission to the Sponsor.
- The investigator will attempt to establish a diagnosis of the event based on signs, symptoms, and/or other clinical information. In such cases, the diagnosis (not the individual signs/symptoms) will be documented as the AE/SAE.

Assessment of intensity/toxicity

- An event is defined as “serious” when it meets at least 1 of the predefined outcomes as described in the definition of an SAE, not when it is rated as severe.
- The investigator will make an assessment of intensity for each AE and SAE (and other reportable safety event) reported during the study and assign it to 1 of the following categories:
 - Mild: An event that is easily tolerated by the participant, causing minimal discomfort and not interfering with everyday activities (for pediatric studies, awareness of symptoms, but easily tolerated).
 - Moderate: An event that causes sufficient discomfort to interfere with normal everyday activities (for pediatric studies definitely acting like something is wrong).
 - Severe: An event that prevents normal everyday activities. An AE that is assessed as severe should not be confused with an SAE. Severe is a category utilized for rating the intensity of an event; and both AE and SAE can be assessed as severe (for pediatric studies, extremely distressed or unable to do usual activities).
- Injection site erythema/redness or swelling from the day of vaccination through Day 5 postvaccination will be evaluated by maximum size.
- The investigator will make an assessment of toxicity for each AE and SAE (and other reportable event) reported during the study. A toxicity grade will be assigned to injection-site AEs, specific systemic AEs, other systemic AEs, and vital sign (temperature) AEs as shown in the following tables. The toxicity grading scales used in this study are adapted from the “FDA Guidance for Industry: Toxicity Grading Scale for Healthy Adult and Adolescent Volunteers Enrolled in Preventive Vaccine Clinical Trials, September 2007.”

- **Injection-Site AE Toxicity Grading Scale**

Injection Site Reaction to Study Vaccine/Placebo ^a	Grade 1	Grade 2	Grade 3	Grade 4
Injection-site AEs occurring Days 1 through 5 following receipt of study vaccine/placebo				
Pain/Tenderness	Does not interfere with activity	Repeated use of non-narcotic pain reliever >24 hours or interferes with activity	Any use of narcotic pain reliever or prevents daily activity	ER visit or hospitalization
Erythema/Redness	Size measured as B	Size measured as C or D	Size measured as E→	Necrosis or exfoliative dermatitis or results in ER visit or hospitalization
Induration/Swelling	Size measured as B	Size measured as C or D	Size measured as E→	Necrosis or ER visit or hospitalization
Other	Does not interfere with activity	Repeated use of non-narcotic pain reliever >24 hours or interferes with activity	Any use of narcotic pain reliever or prevents daily activity	ER visit or hospitalization
Any injection-site reaction that begins ≥6 days after receipt of study vaccine/placebo				
Pain/tenderness Erythema/Redness Induration/Swelling Other	Does not interfere with activity	Repeated use of non-narcotic pain reliever >24 hours or interferes with activity	Any use of narcotic pain reliever or prevents daily activity	ER visit or hospitalization

Abbreviations: AE = adverse event; ER = emergency room; eVRC = electronic Vaccine Report Card.

^a Based upon information provided by the participant on the eVRC and verbally during VRC review. Erythema/Redness and Induration/Swelling are specific injection-site AEs with size designations of letters A through E→, based upon a graphic in the eVRC. Size A is not assigned a toxicity grade; however, injection-site AEs that measure size A should be reported as adverse experiences. If the participant has an ER visit or is hospitalized for any injection-site AE, that AE is to be assigned a toxicity grade of 4, regardless of the size measured.

Specific Systemic AE Toxicity Grading Scale

Systemic (General)	Mild (Grade 1)	Moderate (Grade 2)	Severe (Grade 3)	Potentially Life Threatening (Grade 4)
Headache	No interference with activity	Repeated use of non-narcotic pain reliever >24 hours or some interference with activity	Significant; any use of narcotic pain reliever or prevents daily activity	ER visit or hospitalization
Fatigue	No interference with activity	Some interference with activity	Significant; prevents daily activity	ER visit or hospitalization
Myalgia	No interference with activity	Some interference with activity	Significant; prevents daily activity	ER visit or hospitalization

Abbreviation: AE = adverse event; ER = emergency room.

Other Systemic AE Toxicity Grading Scale

Systemic Illness ^a	Mild (Grade 1)	Moderate (Grade 2)	Severe (Grade 3)	Potentially Life Threatening (Grade 4) ^b
Illness or clinical AE (as defined according to applicable regulations)	No interference with activity	Some interference with activity not requiring medical intervention	Prevents daily activity and required medical intervention	ER visit or hospitalization

Abbreviations: AE = adverse event; ER = emergency room; eVRC = electronic Vaccine Report Card; SAE = serious adverse event.

^a Based upon information provided by the patient on the eVRC and verbally during the eVRC review during the primary safety follow-up period. For SAEs reported beyond the primary safety follow-up period, grading will be based upon the initial report and/or follow-up of the event.

^b AEs resulting in death will be assessed as Grade 4.

Vital Sign (Temperature) Toxicity Grading Scale

Vital Signs ^a	Mild (Grade 1)	Moderate (Grade 2)	Severe (Grade 3)	Potentially Life Threatening (Grade 4)
Fever (°C) ^b (°F) ^b	38.0 to 38.4 100.4 to 101.1	38.5 to 38.9 101.2 to 102.0	39.0 to 40.0 102.1 to 104.0	>40.0 >104.0

^a Participant should be at rest for all vital sign requirements.

^b Oral temperature; no recent hot or cold beverages or smoking.

Assessment of causality

- Did the Sponsor's product cause the AE?
- The determination of the likelihood that the Sponsor's product caused the AE will be provided by an investigator who is a qualified physician. The investigator's signed/dated initials on the source document or worksheet that supports the causality noted on the AE form, ensures that a medically qualified assessment of causality was done. This initialled document must be retained for the required regulatory time frame. The criteria below are intended as reference guidelines to assist the investigator in assessing the likelihood of a relationship between the test product and the AE based upon the available information.
- **The following components are to be used to assess the relationship between the Sponsor's product and the AE;** the greater the correlation with the components and their respective elements (in number and/or intensity), the more likely the Sponsor's product caused the AE:
 - **Exposure:** Is there evidence that the participant was actually exposed to the Sponsor's product such as: reliable history, acceptable compliance assessment (diary, etc.), seroconversion or identification of vaccine virus in bodily specimen?
 - **Time Course:** Did the AE follow in a reasonable temporal sequence from administration of the Sponsor's product? Is the time of onset of the AE compatible with a vaccine-induced effect?
 - **Likely Cause:** Is the AE not reasonably explained by another etiology such as underlying disease, other drug(s)/vaccine(s), or other host or environmental factors?
 - **Rechallenge:** Was the participant re-exposed to the Sponsor's product in the study?
 - If yes, did the AE recur or worsen?
 - If yes, this is a positive rechallenge.
 - If no, this is a negative rechallenge.

(Note: This criterion is not applicable if: (1) the initial AE resulted in death or permanent disability, or (2) the study is a single-dose vaccine study; or (3) Sponsor's product(s) is/are used only 1 time.)

NOTE: IF A RECHALLENGE IS PLANNED FOR AN AE THAT WAS SERIOUS AND MAY HAVE BEEN CAUSED BY THE SPONSOR'S PRODUCT, OR IF RE-EXPOSURE TO THE SPONSOR'S PRODUCT POSES ADDITIONAL POTENTIAL SIGNIFICANT RISK TO THE PARTICIPANT THEN THE RECHALLENGE MUST BE APPROVED IN ADVANCE BY THE SPONSOR CLINICAL DIRECTOR, AND IF REQUIRED, THE IRB/IEC.

- **Consistency with study intervention profile:** Is the clinical/pathological presentation of the AE consistent with previous knowledge regarding the Sponsor's product or drug class pharmacology or toxicology?
- The assessment of relationship will be reported on the CRFs/worksheets by an investigator who is a qualified physician according to his/her best clinical judgment, including consideration of the above elements.
- Use the following scale of criteria as guidance (not all criteria must be present to be indicative of a Sponsor's product relationship).
 - Yes, there is a reasonable possibility of Sponsor's product relationship:
 - There is evidence of exposure to the Sponsor's product. The temporal sequence of the AE onset relative to the administration of the Sponsor's product is reasonable. The AE is more likely explained by the Sponsor's product than by another cause.
- No, there is not a reasonable possibility of Sponsor's product relationship:
 - Participant did not receive the Sponsor's product OR temporal sequence of the AE onset relative to administration of the Sponsor's product is not reasonable OR the AE is more likely explained by another cause than the Sponsor's product. (Also entered for a participant with overdose without an associated AE.)

- For each AE/SAE, the investigator must document in the medical notes that he/she has reviewed the AE/SAE and has provided an assessment of causality.
- There may be situations in which an SAE has occurred and the investigator has minimal information to include in the initial report to the Sponsor. However, it is very important that the investigator always make an assessment of causality for every event before the initial transmission of the SAE data to the Sponsor.
- The investigator may change his/her opinion of causality in light of follow-up information and send an SAE follow-up report with the updated causality assessment.
- The causality assessment is 1 of the criteria used when determining regulatory reporting requirements.

Follow-up of AE and SAE

- The investigator is obligated to perform or arrange for the conduct of supplemental measurements and/or evaluations as medically indicated or as requested by Sponsor to elucidate the nature and/or causality of the AE or SAE as fully as possible. This may include additional laboratory tests or investigations, histopathological examinations, or consultation with other health care professionals.
- New or updated information will be recorded in the CRF.

- The investigator will submit any updated SAE data to the Sponsor within 24 hours of receipt of the information.

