8.1.9 Electronic Vaccination Report Card (eVRC)

The eVRC was developed to be administered electronically via a hand-held device. This item was structured as recommended in the final Food and Drug Administration Patient-Reported Outcome Guidance [U.S. Food and Drug Administration 2009]. The investigator or delegate will train the participant in the use of the eVRC at Visit 1 (Day 1).

Temperatures, injection-site reactions, vaccine-specific complaints, other complaints or illnesses, and concomitant medications or vaccinations will be recorded on the eVRC as

described in Section 1.3 and Section 8.3.4. The investigator or delegate will review the data captured on the eVRC with the participant at the Telephone Contact (Day 15) and Visit 2 (Day 30).

Any differences between eVRC data and the clinical database must be clearly explained in the participant's source documentation.

For the specific AEs collected via the eVRC, the investigator will use the information provided by the participant both on the eVRC and verbally at the time of eVRC review to apply the appropriate assessment of intensity and toxicity as described in Appendix 3.

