8.3.4 Safety Assessments and Use of the eVRC

All participants will be observed for at least 30 minutes after each vaccination for any immediate reactions. If any immediate AEs are observed during this period, the time at which the event occurred within this timeframe, as well as the event itself, any concomitant medications that were administered, and resolution of the event must be recorded on the appropriate eCRF.

Participants will use the eVRC (Section 8.1.9) to document the following information:

- Oral body temperatures measured Day 1 (day of vaccination) through Day 5 postvaccination
- Solicited injection-site AEs (redness/erythema, swelling, and tenderness/pain) Day 1 through Day 5 postvaccination
- Solicited systemic AEs (muscle pain/myalgia, joint pain/arthralgia, headache, and tiredness/fatigue) Day 1 through Day 14 postvaccination
- Any other injection-site or systemic AEs Day 1 through Day 14 postvaccination
- Concomitant medications and nonstudy vaccinations Day 1 to Day 14 postvaccination

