9.4.2 Safety Endpoints

The safety analysis endpoints include:

- Proportion of participants with solicited injection-site AEs (redness/erythema, swelling, and tenderness/pain) from Day 1 through Day 5 postvaccination
- Proportion of participants with solicited systemic AEs (muscle pain/myalgia, joint pain/arthralgia, headache, and tiredness/fatigue) from Day 1 through Day 14 postvaccination
- Proportions of participants with the broad AE categories consisting of any AE and any vaccine-related AE from Day 1 through Day 14 postvaccination
- Proportions of participants with the broad AE categories consisting of any SAE, any vaccine-related SAE, and death from Day 1 through the duration of participation in the study. As this is a single-dose study, the broad AE category of discontinuation of study intervention due to an AE is not applicable.
- Proportion of participants with maximum temperature measurements meeting the Brighton Collaboration cut points from Day 1 through Day 5 postvaccination

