9.6.2 Statistical Methods for Safety Analyses

Safety and tolerability will be assessed by clinical review of all relevant parameters, including AEs and postvaccination temperature measurements.

The analysis of safety results will follow a tiered approach (Table 5). The tiers differ with respect to the analyses that will be performed. AEs (specific terms as well as system organ class [SOC] terms) are either pre-specified as “Tier 1” endpoints or will be classified as belonging to “Tier 2” or “Tier 3” based on the number of events observed.

Tier 1 Events

Safety parameters or AEs of special interest that are identified a priori constitute “Tier 1” safety endpoints that will be subject to inferential testing for statistical significance with p-values and 95% CIs to be provided for between-treatment differences in the proportion of participants with events; these analyses will be performed using the M&N method [Miettinen, O. and Nurminen, M. 1985], an unconditional, asymptotic method. For this protocol, solicited injection-site AEs (redness/erythema, swelling, and tenderness/pain) from Day 1 through Day 5 postvaccination and solicited systemic AEs (muscle pain/myalgia, joint pain/arthritis, headache, and tiredness/fatigue) from Day 1 through Day 14 postvaccination are considered Tier 1 events.

Tier 2 Events

Tier 2 parameters will be assessed via point estimates with 95% CIs provided for differences in the proportion of participants with events (also via the M&N method) [Miettinen, O. and Nurminen, M. 1985].

Membership in Tier 2 requires that at least 4 participants in either treatment group exhibit the event. The threshold of at least 4 events was chosen because the 95% CI for the between-group difference in percent incidence will always include zero when vaccination groups of equal size each have less than 4 events and thus would add little to the interpretation of potentially meaningful differences. Because many 95% CIs for Tier 2 events may be provided without adjustment for multiplicity, the CIs should be regarded as a helpful descriptive measure to be used in review, not a formal method for assessing the statistical significance of the between-group differences in AEs.

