In addition to individual events that occur in 4 or more participants in any vaccination group, the broad AE categories consisting of the proportion of participants with any AE, a vaccine-related AE, an SAE, a vaccine-related SAE, and death will be considered Tier 2 endpoints. Nonserious adverse events (NSAEs) will be followed for 14 days postvaccination and SAEs will be followed for 6 months postvaccination. The proportion of participants with maximum temperature measurements meeting the Brighton Collaboration cut points will also be considered Tier 2 endpoints.

Tier 3 Events

Safety endpoints that are not Tier 1 or 2 events are considered Tier 3 events. Only point estimates by treatment group are provided for Tier 3 safety parameters.

Table 5 Analysis Strategy for Safety Parameters

Safety Tier	Safety Endpoint [†]	p-Value [‡]	95% CI for Between-Group Comparison [‡]	Descriptive Statistics
Tier 1	Injection-site redness/erythema (Days 1 to 5)	X	X	X
	Injection-site swelling (Days 1 to 5)	X	X	X
	Injection-site tenderness/pain (Days 1 to 5)	X	X	X
	Muscle pain/myalgia (Days 1 to 14)	X	X	X
	Joint pain/arthralgia (Days 1 to 14)	X	X	X
	Headache (Days 1 to 14)	X	X	X
	Tiredness/fatigue (Days 1 to 14)	X	X	X
Tier 2	Any AE [†]		X	X
	Any Vaccine-Related AE [†]		X	X
	Any SAE [†]		X	X
	Any Vaccine-Related SAE [†]		X	X
	Death [†]		X	X
	Maximum temperature measurements meeting the Brighton Collaboration cut points (Days 1 to 5)		X	X
	Specific AEs by SOC and PT [§] (incidence ≥ 4 of participants in one of the vaccination groups)		X	X
Tier 3	Specific AEs by SOC and PT [§] (incidence < 4 of participants in all of the vaccination groups)			X
[†] These endpoints are broad AE categories. For example, descriptive statistics for the safety endpoint of “Any AE” will provide the number and percentage of participants with at least 1 AE.				
[‡] These analyses will be performed using the M&N method [Miettinen, O. and Nurminen, M. 1985].				
[§] Includes only those endpoints not prespecified as Tier 1 or not already prespecified as Tier 2 endpoints.				
AE = adverse event; CI = confidence interval; M&N = Miettinen and Nurminen; PT = preferred term; SAE = serious adverse event; SOC = system organ class; X = results will be provided.				

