9.9.2 Sample Size and Power for Safety Analyses

The probability of observing at least 1 SAE in this study depends on the number of participants vaccinated and the underlying incidence of participants with an SAE in the study population. Calculations below assume that 100% of the randomized participants will be evaluable for safety analyses. There is an 80% chance of observing at least 1 SAE among 600 participants in V114 group if the underlying incidence of an SAE is 0.27% (1 of every 373 participants receiving the vaccine). There is a 50% chance of observing at least 1 SAE among 600 participants in the V114 group if the underlying incidence of an SAE is 0.12% (1 of every 866 participants receiving the vaccine). If no SAEs are observed among

600 participants, this study will provide 97.5% confidence that the underlying percentage of participants with an SAE is <0.61% (1 in every 163 participants) in the V114 group.

Table 6 summarizes the percentage point differences between the 2 vaccination groups that could be detected with 80% probability for a variety of hypothetical underlying incidences of an AE.

Table 6 Differences in Incidence of Adverse Event Rates Between the 2 Vaccination Groups That Can be Detected With an Approximately 80% Probability

Incidence of Adverse Event		Risk Difference
V114 (%)	Prevnar 13™ (%)	Percentage Points
1.6	0.1	1.5
5.0	2.0	3.0
9.1	5.0	4.1
15.4	10.0	5.4
21.2	15.0	6.2
26.8	20.0	6.8
37.6	30.0	7.6

The incidences presented here are hypothetical and do not represent actual adverse experiences in either group. The incidences assume a 2-sided 5% alpha level with 600 participants in each group. No multiplicity adjustments were made.
The calculations are based on an asymptotic method proposed by Farrington and Manning (1990) [Farrington, C. P. 1990].

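### Does the missing joint-pain row in the toxicity scale, with no severity summary planned in Section 9, weaken the safety analysis?

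*Combined protocol and SAP*

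**What the plan says.** Section 8.1.9 has the investigator take the participant's electronic report card and verbal account and "apply the appropriate assessment of intensity and toxicity as described in Appendix 3". Appendix 3 (Section 10.3.4) sets out two separate assessments for every AE.

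- **Intensity** is mild, moderate or severe. The top category is "Severe: An event that prevents normal everyday activities", with no condition about treatment.
- **Toxicity grade** runs from 1 to 4, with separate tables for injection-site events, specific systemic events, other systemic events and temperature. The specific systemic table has rows for headache, fatigue and myalgia. In the other systemic table, Grade 3 is "Prevents daily activity and required medical intervention".

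The matching endpoint in Section 9.4.2 is "Proportion of participants with solicited systemic AEs (muscle pain/myalgia, joint pain/arthralgia, headache, and tiredness/fatigue) from Day 1 through Day 14 postvaccination". Section 9.6.2 makes the four systemic complaints and the three injection-site reactions Tier 1 events and compares the proportions of participants affected. A footnote to Table 5 illustrates its descriptive statistics with the any-AE row, which "will provide the number and percentage of participants with at least 1 AE". Section 9.6.2 opens more broadly: "Safety and tolerability will be assessed by clinical review of all relevant parameters, including AEs and postvaccination temperature measurements".

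**The concern.** Joint pain is one of four solicited systemic events and the only one without a row in the specific systemic table. If it is graded on the table for other illness, the label Severe means two different things for the same event: prevented activity on the intensity scale, and prevented activity plus medical intervention on the toxicity scale. An episode of myalgia with the same consequences would be Grade 3 without any intervention.

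Section 9 does not settle which rating counts, because it plans no result by severity for any of the seven Tier 1 events. Safety and tolerability is the first-listed primary objective. Two arms with the same proportion of participants affected but different severity would look alike in every Tier 1 row. If a severity table were added after unblinding, the count of severe joint pain could depend on the scale then chosen.

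**Working it through.** No sample size, power or alpha figure in the plan depends on this point, so the main check is a comparison of texts.

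**1. Which cases lack a grade.** Inputs: the intensity definitions, the other systemic table and the myalgia row, all in Section 10.3.4. That joint pain goes to the other systemic table is an inference; no sentence says so. Three levels of activity limitation, intervention yes or no, and emergency room visit or hospitalization yes or no give 3 × 2 × 2 = 12 cases. In the 6 with an emergency room visit or hospitalization, both toxicity tables give Grade 4. The other 6 are:

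| Activity | Intervention | Intensity | Joint pain, other table | Myalgia row |
|---|---|---|---|---|
| Not affected | No | Mild | 1 | 1 |
| Not affected | Yes | Mild | 1 | 1 |
| Some interference | No | Moderate | 2 | 2 |
| Some interference | Yes | Moderate | none | 2 |
| Prevented | No | Severe | none | 3 |
| Prevented | Yes | Severe | 3 | 3 |

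Two of these 6 cases (2 of all 12) have no toxicity grade. All 12 have an intensity rating.

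**2. Whether the two ratings were meant to agree.** They part company elsewhere too. Any narcotic pain reliever makes headache or injection-site pain Grade 3. Redness and swelling on Days 1 to 5 are graded mainly by size. An emergency room visit gives Grade 4 whatever the intensity. These are two instruments with different criteria, so a difference between them is not in itself a contradiction.

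**3. Whether a planned output uses either rating.**

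- Seven Tier 1 rows: occurrence of the event.
- Five broad Tier 2 categories (any AE, vaccine-related AE, any serious AE (SAE), vaccine-related SAE, death): occurrence, seriousness and causality.
- Maximum temperature: measured values against the Brighton Collaboration cut points.
- Specific AEs in Tiers 2 and 3: occurrence.
- Subgroup summaries in Section 9.10: AEs and solicited AEs, with no grade mentioned.

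Outputs that use a toxicity grade or an intensity rating: none. An event without a grade still counts as an event. Section 10.3.4 treats the smallest redness and swelling that way: they get no grade but are reported.

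**4. Whether Table 6 can size the problem.** Its note says "The incidences assume a 2-sided 5% alpha level with 600 participants in each group". The row 5.0% versus 2.0% reproduces, using power = Φ[(p₁ − p₂ − 1.96·s₀)/s₁]:

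- pooled rate = (0.05 + 0.02)/2 = 0.035
- s₀ = √(2 × 0.035 × 0.965/600) = 0.01061
- s₁ = √[(0.05 × 0.95 + 0.02 × 0.98)/600] = 0.01058
- power = Φ[(0.03 − 1.96 × 0.01061)/0.01058] = Φ(0.87) = 0.808

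This agrees with the stated level of about 80%, but it describes incidence. The documents give no severity rates, so reading these percentages as severe-event rates would be an assumption. It is also true by construction that a test of incidence, with equal incidence in both arms, flags a difference only at about its 5% error rate.

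**The case for a change.** The strongest case for acting is that a primary tolerability objective deserves a severity result fixed in advance, that the data are already collected, and that one descriptive table and one named scale would cost little. Clinical review of all relevant parameters is a general phrase that commits to no table. Section 9 and Section 9.10 mention a supplemental Statistical Analysis Plan, but neither promises a severity summary in it.

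Part of this stands. The text names no scale for analysis, and a table by toxicity grade would have to deal with two undefined cases for joint pain. The share of activity-preventing joint pain that would fall there could be anything from none to all.

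The rest does not carry the weight put on it. Section 3 words the objective in terms of the proportion of participants with AEs, and the planned analyses estimate that. Severe outcomes are not wholly absent either: inpatient admission makes an event serious under Section 10.3.2 (an elective procedure for an unchanged pre-existing condition aside), and SAEs and deaths have Tier 2 rows with 95% confidence intervals. An emergency room visit without admission does not reach those rows on that ground alone. Nor does the gap favour an arm by design, since the grading rules are the same for both arms and blinded site personnel do the safety follow-up (Sections 6.3.3 and 8.1.8).

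A later choice between scales is a fair worry, but an easy one to meet. Intensity is required for every AE, needs no repair and no regrading, and is the natural basis for a summary. Section 9 already lets changes to non-confirmatory analyses be documented before unblinding without a protocol amendment.

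**Conclusion.** No change to the plan follows. The missing joint-pain row is a clerical gap in Appendix 3: it leaves 2 of the 6 cases without an emergency room visit or hospitalization ungraded on the toxicity scale and none unrated on the intensity scale. Its effect on the planned safety results is nil, because no output in Section 9 uses the toxicity grade; the seven Tier 1 comparisons and the Tier 2 intervals are the same whatever grade is entered. The immunogenicity hypotheses, their error rate and the power statements are untouched.

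The lack of a severity table is missing descriptive detail that analysts can supply sensibly from the intensity ratings. It does not make any stated result wrong.

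This rests on two readings: that joint pain is graded on the other systemic table, which is inferred, and that no severity analysis by toxicity grade is specified elsewhere. The data entry guidelines and any supplemental analysis plan are not among the documents. If such an analysis does exist, the solicited-event list and the toxicity tables would need to be reconciled before it is run.
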